3.1 General Design

This will be a Randomized controlled trial, in which a total of 72 subjects will be enrolled at 1 clinical site. Subjects will be randomly assigned to one of two groups (#1, #2), with 36 subjects per group. One group will be given placebo (Vehicle eye drops) and the other group will be given eye drops containing the study drug (rhDNase I 0.1%).

Patients with established oGVHD will be approached by a member of the research staff to determine if he/ she might be interested in participating in a research study. If the subject is interested, the research staff member will describe the study. If the subject is willing to enter the study, the study will be discussed and the subject will be asked to sign the informed consent form. Consent will be obtained prior to screening to determine eligibility. Screening procedures include documentation of definite oGVHD. Eligible subjects will be enrolled in the study.

All enrolled subjects will receive their first dose of test medication (placebo/ study drug) on study Day 1 in the doctor's office, and after completion of the study assessments, will have the topical eye drops dispensed for self-administration. See Section 5.4 *Preparation and Administration of Study Drug* for details.

Subjects will be provided with diaries to record the time of each dose and will also be asked to record any adverse symptoms. In addition, they will be asked to make a note of any missed doses together with the reason for the omission. Subjects will return two weeks later on Day 14 for further study assessments, thereafter at 4 weeks, 6 weeks and 8 weeks (the last day of treatment), and again at 10 weeks after two weeks of no treatment with study drug for the final study assessments.

Because NETs have an important role in the innate defense against microbes,³⁵ treatment with DNase I to clear NETs may increase susceptibility to ocular surface infections. Symptom relief is an important goal in patients having dry eyes, with the proviso that treatment does not interfere with pathogen defense. Therefore, we will determine whether DNase I treatment affects the ocular surface microbiome.

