4.1 Inclusion Criteria

The PI and other members of International Chronic Ocular GVHD Consensus Group have established the consensus diagnostic criteria and classification for chronic ocular GVHD.⁴⁰

Table 1: Severity scale in chronic ocular GVHD

Severity scores (points)	Schirmer's test (mm)	CFS (points)	OSDI (points)	Conj (points)
0	>15	0	<13	None
1	11–15	<2	13–22	Mild/Moderate

Severity scores (points)	Schirmer's test (mm)	CFS (points)	OSDI (points)	Conj (points)
2	6–10	2–3	23–32	Severe
3	≤5	≥4	≥33	

CFS; corneal fluorescein staining, OSDI; Ocular Surface Disease Index. Conj; conjunctival injection. Severity classification; Total score (points); (Schirmer's test score+ CFS score+ OSDI score+ Conj injection score) = None;0–4, Mild/Moderate; 5–8, Severe, 9–11.

Table 2: Diagnosis of chronic ocular GVHD

	None (points)	Probable GVHD (points)	Definite GVHD (points)
Systemic GVHD(-)	0–5	6–7	≥8
Systemic GVHD(+)	0–3	4–5	≥6

Based on these criteria (Tables 1 and 2),⁴⁰ patients with definite ocular GVHD will be enrolled. Additionally, all of the following criteria should be met to be eligible for the study:

- Aged 18 years or older.
- Capable of giving informed consent and does provide informed consent.
- Schirmer I <10
- Corneal/ conjunctival (Fluorescein and Lissamine Dye) staining ≥1
- Ocular symptoms must be considered as annoying or activity limiting (OSDI ≥13; mild).
- Women must be post-menopausal ≥ 1 year, or surgically sterilized. If not, a negative urine pregnancy test is required within 14 days of receiving her first dose of test medication (placebo/ study drug) along with definite evidence of contraceptive use during the duration of the study. Women of reproductive age should use a method of birth control that is acceptable to the subject and the study doctor. This may include oral contraceptive pills, birth control implants, barrier methods or abstinence. If a subject mentions she suspects she may be pregnant after being enrolled, another pregnancy test will be administered. If the test is positive, she will be discontinued from the study immediately.

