6.5.6 Visit 6: Week 8 (± 2 days)

Treatment Visit (after any dose for that day)

- Vital Signs
- OSDI
- Fluorescein and Lissamine Dye staining, and Schirmer 1 test
- Keratograph Oculus Redness Score
 - > Non-invasive Keratography Tear Film Break-up Time (NIKBUT)
 - > Tear Meniscus Height (TMH)
- TearLab Osmolarity Test
- InflammaDry Test for MMP-9 Protein
- Clinical Global Impression, Subject Global Assessment
- Test Substance Tolerance (VAS)
- Ophthalmic Examination (slit lamp examination, Ocular surface redness score)
- Tear fluid collection for analysis (PicoGreen, Cellometry)
- Physical Inspection of the Nose and Oropharynx
- Conjunctival and eyelid margin cultures
- Review the subject's diary and record changes in concomitant medication, deviations from drug schedule and adverse events.

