6.5.7 Visit 7: Week 10 (± 2 days)

Follow-Up Visit

- Vital Signs
- BSCVA (Snellen's chart)
- OSDI
- Clinical Global Impression, Subject Global Assessment
- Ophthalmic Examination (slit lamp examination, Ocular surface redness score)
- Physical Inspection of the Nose and Oropharynx
- Record changes in concomitant medication and adverse events.

7 Statistical Plan

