All AEs and SAEs whether volunteered by the subject, discovered by study personnel during questioning, or detected through physical examination, laboratory test, or other means will be reported appropriately. For each adverse event, the following information will be recorded on the subject's Case Report Form(s): onset date, end date or continues, intensity, duration, relationship to test patch, action taken, and outcome. If a subject experiences a serious adverse event (SAE), study staff may discontinue the subject from study participation. The study staff must notify the IRB within 24 hours of receipt of the information. The study staff will instruct the subject to notify the research facility should any adverse event occur within 7 days of study completion. (For definitions of an AE and SAE, see below). Subjects who withdraw due to an adverse event may be replaced.

- Serious Adverse Event: An AE should be classified as an SAE if the following criteria are met:
 - 1. It results in death (i.e., the AE actually causes or leads to death.).
 - 2. It is life-threatening (i.e., the AE, in the view of the investigator, places the subject at immediate risk of death. It does not include an AE that, had it occurred in a more severe form, might have caused death.).
 - 3. It requires or prolongs inpatient hospitalization.
 - 4. It results in persistent or significant disability/incapacity (i.e., the AE results in substantial disruption of the subject's ability to conduct normal life functions).
 - 5. It results in a congenital anomaly/ birth defect in a neonate/infant born to a mother exposed to the investigational medicinal product (IMP).
 - 6. It is considered a significant medical event by the investigator based on medical judgement (e.g., my jeopardize the subject or may requires medical or surgical intervention to prevent any of the occurrences listed above.

To ensure consistency of AE and SAE causality assessments, the following general guideline will be applied:

Yes

There is a plausible temporal relationship between the onset of the AE and administration of the Pulmozyme, and the AE cannot be readily explained by the subject's clinical state, intercurrent illness, or concomitant therapies; and/or the AE follows a known pattern of response to the Pulmozyme; and/or the AE abates or resolves upon discontinuation of the Pulmozyme or dose reduction and, if applicable, reappears upon re-challenge

No

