- Hospitalization or prolonged hospitalization required to allow efficacy measurement for the study or
- Hospitalization or prolonged hospitalization for scheduled therapy of the target disease of the study.

e. Pregnancy

If a female subject becomes pregnant while receiving the study drug or within 30 days after the last dose of study drug, a report will be completed and expeditiously submitted to Genentech, Inc. Follow-up to obtain the outcome of the pregnancy will also occur. Abortion, whether accidental, therapeutic, or spontaneous, should always be classified as serious, and expeditiously reported as an SAE. Similarly, any congenital anomaly/birth defect in a child born to a female subject exposed to the {study drug} should be reported as an SAE.

Additional information on any Pulmozyme (rhDNase)-exposed pregnancy and infant will be requested by Roche Drug Safety at specific time points (i.e. after having received the initial report, at the end of the second trimester, 2 weeks after the expected date of delivery, and at 3, 6, and 12 months of the infant's life).

f. Post-Study Adverse Events

The investigator should expeditiously report any SAE occurring after a subject has completed or discontinued study participation if attributed to prior {study drug} exposure. If the investigator should become aware of the development of cancer or a congenital anomaly in a subsequently conceived offspring of a female subject who participated in the study, this should be reported as an SAE.

g. Reconciliation

The Sponsor agrees to conduct reconciliation for the product. Genentech and the Sponsor will agree to the reconciliation periodicity and format, but agree at minimum to exchange quarterly (no less frequently than monthly) line listings of cases received by the other party. If discrepancies are identified, the Sponsor and Genentech will cooperate in resolving the discrepancies. The responsible individuals for each party shall handle the matter on a case-by-case basis until satisfactory resolution. The sponsor shall receive reconciliation guidance documents within the 'Activation Package'.

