8.5.3 Adverse Event Reporting

All subjects who have been exposed to study drug will be evaluated for adverse events. The study period during which all AEs and SAEs will be reported begins after informed consent is obtained and initiation of study treatment and ends 21 days following the last administration of study treatment or study discontinuation/termination, whichever is earlier. AE reports and annual summaries will not include subject identifiable material. Each report will only include the identification code. All adverse events will be evaluated beginning with onset, and evaluation will continue until resolution is noted, or until the Investigator determines that the subject's condition is stable, whichever is earlier. The Investigator will take all appropriate and necessary therapeutic measures required for resolution of the adverse event. Any medication necessary for the treatment of an adverse event must be recorded on the concomitant medication case report form. If more than one distinct adverse event occurs, each event should be recorded separately. Procedures such as surgery should not be recorded as adverse events. However, the medical condition for which the procedure was performed should be reported if it meets the definition of adverse event as described previously.

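### Pregnancies are reportable to 30 days after the last dose, but the visible protocol has no scheduled or pregnancy-specific way of learning of one after week 10, so ascertainment is incomplete

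*Combined protocol and SAP*

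**What the plan says.** Section 8.5.2(e) defines the reportable case as a woman who "becomes pregnant while receiving the study drug or within 30 days after the last dose of study drug". A report goes to the manufacturer and the outcome is to be followed. Section 8.6.2 times transmission of a pregnancy report from the date of awareness, and qualifies follow-up to outcome as being done where it is possible.

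The visit plan is shorter. Section 3.1 makes week 8 the last day of treatment, and subjects return "again at 10 weeks after two weeks of no treatment with study drug for the final study assessments". Sections 6.5.6 and 6.5.7 allow 2 days either way on the week 8 and week 10 visits. Neither lists a pregnancy test. The schedule of visits and section 6.5.1 place the only scheduled test at screening. Section 4.1 adds a repeat test for a woman who tells the site, once enrolled, that she suspects pregnancy.

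Three other periods bear on the point:
- **Post-study instruction (8.1):** subjects are told to notify the site "should any adverse event occur within 7 days of study completion".
- **AE/SAE reporting period (8.5.3):** it "ends 21 days following the last administration of study treatment", or sooner if participation or the study stops first.
- **Contraception (4.1):** women of reproductive age need "definite evidence of contraceptive use during the duration of the study". The synopsis gives the study duration as 10 weeks.

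**The concern.** The protocol declares a 30-day window for pregnancies, but its other follow-up periods stop short of day 30 and none of them is written with pregnancy in mind. After week 10 no visit, test or call is scheduled. The one remaining instruction asks about adverse events, and a woman may not think of a pregnancy as an adverse event.

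A conception late in treatment that is not yet recognised at week 10, or one in the weeks after dosing, would then come to light only if the woman contacted the site unasked. A final report of no exposed pregnancies could not be told apart from one in which nobody asked across the declared window. In a first randomised trial of this route of administration, that weakens the safety record, though not the efficacy analysis.

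**Working it through.** **Inputs.** Last dose at week 8, day 56 (3.1). Final visit at week 10, day 70 (3.1, 6.5.7). Window of 2 days either way on each visit (6.5.6, 6.5.7). Pregnancy window 30 days after the last dose (8.5.2(e)). Post-completion instruction 7 days (8.1). AE/SAE period at most 21 days after the last dose (8.5.3). I take the last dose to fall on the day of the week 8 visit, and study completion to be the week 10 visit.

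**Step 1: the plan's own interval.** 70 − 56 = 14 days. This reproduces the two weeks off drug in section 3.1.

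**Step 2: visit windows.** The week 8 visit falls on days 54 to 58 and the week 10 visit on days 68 to 72.
- Shortest interval: 68 − 58 = 10 days.
- Longest interval: 72 − 54 = 18 days.

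**Step 3: uncovered part of the 30 days.** With g the days from last dose to final visit, the time with no visit is 30 − g. The time beyond the 7-day instruction as well is 30 − (g + 7).

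| g (days) | No visit: 30 − g | Instruction ends: g + 7 | No instruction: 30 − (g + 7) |
|---|---|---|---|
| 10 | 20 | day 17 | 13 |
| 14 (nominal) | 16 | day 21 | 9 |
| 18 | 12 | day 25 | 5 |

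**Step 4: AE/SAE period.** 30 − 21 = 9 days, the same nominal shortfall.

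**Step 5: early withdrawal.** Section 4.4.2 asks a woman who leaves before week 8 to complete the week 10 procedures as soon as possible. If that visit falls g days after her last dose, the same formulas apply with a smaller g. At the limit g = 0, 30 days have no visit and 30 − 7 = 23 have no instruction. The documents give no typical g, so this is a bound.

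**Step 6: how the periods fit together.** Section 8.5.2(e) classes every abortion as a serious event to be reported. Section 8.5.3 closes AE and SAE reporting by day 21 at the latest, and 8.5.2(f) reopens it for serious events only if they are attributed to the drug. An abortion after a conception on days 22 to 30 would fall outside the period in 8.5.3. Unless it were attributed to the drug, it would be captured only by reading 8.5.2(e) as overriding that limit, which the text does not say.

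**The case against.** The best defence is that the pregnancy duty is conditional and passive. It applies if a pregnancy occurs and the site becomes aware of it. The reporting clock in section 8.6.2 starts at awareness, and follow-up of a known pregnancy runs outside the visit schedule, with information requested up to 12 months of the infant's life. Nothing requires active screening to day 30. This stands, and it defeats the tempting inference that the protocol's follow-up cannot be met.

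Other stronger readings also fail:
- **That no instruction applies after week 10.** The 7-day instruction in 8.1 does apply, to adverse events.
- **That section 8.6.2 takes pregnancy out of adverse events altogether.** It says only that pregnancy reports are not in themselves serious events or adverse drug reactions. A subject might therefore read the 7-day instruction as including pregnancy, but it does not say so.
- **That the repeat test is confined to the visit period.** Section 4.1 gives it no end date.
- **That a contraception period shorter than the reporting window is a contradiction.** The two can serve different purposes. The mismatch needs an explanation from the sponsor, but the text does not show that either is wrong.

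Three further points have some weight. Section 8.5.1 requires open health questions at every evaluation, so a pregnancy already recognised by week 10 may come up there, although no question names it. Section 4.4 allows safety follow-up of withdrawn subjects where possible. The consent pages are not available for review and may carry a pregnancy instruction.

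None of these supplies a scheduled or pregnancy-specific step between week 10 and day 30 in the visible protocol.

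**Conclusion.** The point holds as a gap in ascertainment. Nominally 16 of the 30 days after the last dose (12 to 20) have no visit, and 9 (5 to 13) have no instruction of any kind. The gap is longer for some early withdrawals. Pregnancies that the site hears of can be reported and followed. Those it does not hear of would be missed.

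The consequence is small. The number of women of reproductive potential is not given, only 36 of the 72 subjects receive the drug, and entry requires a negative test and contraception for such women, so very few events are likely. Sample size, power and the efficacy analysis are untouched. The change is still worth making because it is nearly free and the window is the protocol's own.

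The conclusion assumes that dosing ends on the day of the week 8 visit, that study completion means the week 10 visit, and that the consent form does not already contain the missing instruction.

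**What to change.** 1. In section 8.1, extend the existing call-back instruction for women of reproductive potential so that it names pregnancy and runs to 30 days after the last dose. Give the instruction at Visit 7 or, for those who leave early, at the early-withdrawal visit.
2. Add one telephone contact with these women at 30 days after the last dose. Make it in both arms, since staff are masked, and record the answer so that a count of zero rests on a question asked.
3. Have the sponsor reconcile the contraception period in section 4.1, the 21-day AE/SAE period in section 8.5.3 and the 30-day window in section 8.5.2(e). How long contraception should last is for the sponsor's clinicians.
4. Check that the consent form carries the same instruction.

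The cost is one call per woman of reproductive potential and a few lines of protocol text, with no extra visit.

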8.5.3 Adverse Event Reporting

All subjects who have been exposed to study drug will be evaluated for adverse events. The study period during which all AEs and SAEs will be reported begins after informed consent is obtained and initiation of study treatment and ends 21 days following the last administration of study treatment or study discontinuation/termination, whichever is earlier. AE reports and annual summaries will not include subject identifiable material. Each report will only include the identification code. All adverse events will be evaluated beginning with onset, and evaluation will continue until resolution is noted, or until the Investigator determines that the subject's condition is stable, whichever is earlier. The Investigator will take all appropriate and necessary therapeutic measures required for resolution of the adverse event. Any medication necessary for the treatment of an adverse event must be recorded on the concomitant medication case report form. If more than one distinct adverse event occurs, each event should be recorded separately. Procedures such as surgery should not be recorded as adverse events. However, the medical condition for which the procedure was performed should be reported if it meets the definition of adverse event as described previously.

8.6 Adverse Event Reporting

8.6.1 AEs of Special Interest (AESIs)

AEs of Special Interest are defined as a potential safety problem, identified as a result of safety monitoring of the Product. There are no AESIs for pulmozyme.

8.6.2 Adverse Event Reporting

Investigator will report all SAEs to FDA, IRB, NEI, and Genentech within the timelines described below. The completed MedWatch/case report will be faxed immediately upon completion to Genentech Drug Safety at:

[contact] OR [contact]

Serious adverse events (SAEs), pregnancy reports and AEs of special interest (AESIs), where the patient has been exposed to the Product, will be sent on a MedWatch or CIOMS I form to the Roche contact. Transmission of these reports (initial and follow-up) will be either electronically or by fax and within the timelines specified below:

SADRs

Serious AE reports that are related to the Product shall be transmitted to Roche within fifteen (15) calendar days of the awareness date.

Other SAEs

Serious AE reports that are unrelated to the Product shall be transmitted to Roche within thirty (30) calendar days of the awareness date.

Pregnancy reports

While such reports are not serious AEs or ADRs per se, as defined herein, any reports of pregnancy, where the fetus may have been exposed to the Product, shall be transmitted to Roche within thirty (30) calendar days of the awareness date. Pregnancies will be followed up until the outcome of the pregnancy is known, whenever possible, based upon due diligence taken to obtain the follow-up information.

Special situation reports

In addition to all AEs, pregnancy reports and AESIs, the following Special Situations Reports should be collected and transmitted to Roche even in the absence of an Adverse Event within thirty (30) calendar days:

- Data related to the Product usage during pregnancy or breastfeeding
- Data related to overdose, abuse, off-label use, misuse, inadvertent/erroneous administration, medication error
 or occupational exposure, with or without association with an AE/SAE unless otherwise specified in the
 protocol
- Data related to a suspected transmission of an infectious agent via a medicinal product (STIAMP)
- Lack of therapeutic efficacy

In addition, reasonable attempts will be made to obtain and submit the age or age group of the patient, in order to be able to identify potential safety signals specific to a particular population.

Aggregate Reports

[name] will forward a copy of the Publication to Roche upon completion of the Study.

8.6.3 MedWatch 3500A Reporting Guidelines

In addition to completing appropriate patient demographic and suspect medication information, the report should include the following information within the Event Description (section 5) of the MedWatch 3500A form:

- Protocol description (and number, if assigned)
- Description of event, severity, treatment, and outcome if known
- Supportive laboratory results and diagnostics
- Investigator's assessment of the relationship of the adverse event to each investigational product and suspect medication

